**Ketone monitoring:**

Blood or urine ketones are checked when BG readings are > 250 or with complaints of illness. Blood ketone results are preferred when a camper is on Depokote, and cases of suspected diabetes ketoacidosis.

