**Hyperglycemia management, BG is  $\geq$ 250 mg/dl:**

- Check ketones (urine or blood)
- Negative ketones (trace urine ketones, < 0.6 mmol/l blood ketones)
  - Give a correction to the ordered target (typically 120–150) and increase fluids

- May continue activity
- Recheck in 1 hour If the blood sugar is coming down, recheck in another hour until BG < 250 mg/dl.
- If the blood sugar is going up, give the correction by injection and change the pump site
- Positive ketones (small urine ketones or  $\geq 0.6$  mmol/l blood)
  - Change the pump site and increase fluids.
  - Give insulin correction by injection to ordered target (typically 120–150 mg/dl).
  - Obtain hourly blood glucose readings.
  - Discontinue activity until ketones have cleared
  - Notify the physician of blood sugar reading >300 mg/dl and anytime there are positive ketones.

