- There is no area of the camp that is commonly visited by campers that is more than ~ 300 yards from any other area, so it will be easy for study staff to circulate and to get from one area to another if needed. Under the unusual circumstances when campers go further than this (i.e. for a hike) a study staff member will accompany that group carrying all needed supplies (which will also be duplicated by the camp RN/NG who will also accompany such groups. The remaining members of the study team will remain at the main camp area, maintaining the same ratio of study staff to subjects.
- Before disconnecting from the device for shower:
 

BG	Treatment
< 100 mg/dl	15g rapid acting carbohydrate
- Over the next five days (3:00 PM Sunday to 3:00 PM Friday) the bionic pancreas will control insulin and glucagon dosing and the volunteers will otherwise be treated according to camp guidelines except for specifically noted exceptions in the protocol.
- During closed-loop control the glucose measurements from the CGM will be transmitted to the bionic pancreas. The control algorithm will respond by commanding SC doses of insulin and/or glucagon as appropriate through the Tandem t:slim pumps.
- During the experiment the bionic pancreas device will be worn by the volunteer or kept nearby (such as when sleeping) at all times to ensure good radio-frequency signal reception. The device may be removed for short periods of time (no more than 30 minutes) for showering and swimming.
- If during the course of an experiment, a DexCom G4 sensor fails (reports sensor failure, ceases to transmit data, reports multiple calibration failures, or reports questionable data), the bionic

pancreas will automatically switch to giving basal insulin based on historical basal insulin needs at that time of the day. In addition, any BG measurements entered into the bionic pancreas will be used to dose insulin and glucagon as if they were CGM values and the system will continue to accept meal announcements. A new sensor will be inserted and closed-loop control will automatically resume once the new sensor is initially calibrated.

- Meals will be announced to the control algorithm 15-20 minutes prior to the meal at the same time as meal boluses are delivered for other campers. Low BG will be treated as usual, except that no action will be taken for  $BG > 70$  mg/dl.

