- Regardless of location, camp healthcare providers will be able to reach volunteers on short notice. Camp healthcare providers will have basic training on the closed-loop system and the key elements of the protocol. They will keep a charged cell phone with them at all times. If they have a question they will be able to immediately contact study personnel monitoring remotely. If the question or issue cannot be resolved over the phone, a study staff “runner” will be sent to the location. If there is a medical problem that cannot be resolved according to study protocol or camp medical procedures, they will call 911 immediately and provide their location.
- The camp healthcare provider will carry carbohydrates for hypoglycemia treatment and glucagon rescue kits for hypoglycemic emergencies. The central monitoring site will have spare insulin lispro in a cold pack, spare pump supplies, spare DexCom G4 sensors and transmitters,

and spare bionic pancreas control units. If there is a problem with the closed-loop device, study staff will be called and will troubleshoot the system or replace devices as needed.

- Camp healthcare provider's or counselors for each cabin will assist campers as required to announce their meals to the bionic pancreas by indicating approximate meal size on one of the input screens on the device interface. The indicated meal size will be based on the report of typical meal sizes from the volunteer and their parents, study-specific information obtained during the check-in process, and the number of carbohydrates chosen by the volunteer for that meal. The bionic pancreas will then provide some of the insulin for the meal. The algorithm chooses the meal-priming bolus size using an adaptive algorithm that attempts to provide 75% of the insulin for meals of a similar size eaten at the same time of day in the past. The initial parameters are conservative and weight based and adapt over time.
- Camp healthcare providers and counselors will carry any snack items needed for hypoglycemia. Study staff following patients will also have emergency supplies available including oral carbohydrates and glucagon kits.

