#### **V. f. Response to Hyperglycemia**

- Any time a ketone check is mandated by camp protocol the closed-loop system will be checked for any malfunction and any such problems will be corrected. The insulin infusion set will be replaced if mandated by camp protocol or if there is any doubt as to its proper functioning.
- If no correctable fault is found, but there is doubt regarding the correct function of the bionic pancreas system, an entirely new backup bionic pancreas system may be started.
- While the new system is being replaced and calibrated the volunteer will use their own pump in open loop mode according to usual care camp protocols.
- If the blood ketone result is  $\geq 0.6$ mmol/dL a study physician or nurse practitioner will be notified and will evaluate the volunteer in person.

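### The blood-ketone trigger for an in-person study-clinician visit is printed as 0.6 mmol/dL (6.0 mmol/L), ten times the camp's 0.6 mmol/l positive cut-off

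*Combined protocol and SAP*

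**What the plan says.** Two places in the supplied text give a blood-ketone cut-off.

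- **Study rule, section V. f. (Response to Hyperglycemia).** At a blood ketone result of ≥ 0.6 "mmol/dL a study physician or nurse practitioner will be notified and will evaluate the volunteer in person". This is the only study-specific ketone action level in the protocol.
- **Camp rule, section V. d. ii. (Hyperglycemia management).** The lower branch is "Negative ketones (trace urine ketones, < 0.6 mmol/l blood ketones"; the upper branch is "Positive ketones (small urine ketones or" a blood value of ≥ 0.6 mmol/l. The upper branch brings a pump-site change, extra fluids, a correction dose by injection, hourly glucose readings and a stop to activity, and adds: "Notify the physician of blood sugar reading >300 mg/dl and anytime there are positive ketones".

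The two rules are linked. Under Ketone monitoring in section V. d. ii., "Blood or urine ketones are checked when BG readings are > 250 or with complaints of illness". Section V. f. builds on those checks: "Any time a ketone check is mandated by camp protocol the closed-loop system will be checked for any malfunction". During the closed-loop period, section V. d. iii. keeps camp care in force: "the volunteers will otherwise be treated according to camp guidelines except for specifically noted exceptions in the protocol".

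**The concern.** The two rules share the numeral 0.6 and the sign ≥ but differ in the volume unit. Nothing in the supplied text states or justifies a higher threshold for calling the study clinician than for calling ketones positive.

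At stake is when a study clinician must see the volunteer. A positive ketone result in a volunteer whose insulin comes from an investigational device raises the question of whether the infusion set or the system has failed. The camp rule requires that a physician be notified, but it does not require that a study clinician attend. Camp staff know the device less well than study staff do: "Camp healthcare providers will have basic training on the closed-loop system and the key elements of the protocol". Applied as printed, the study rule would leave that visit optional over a range that the camp rule already treats as needing action.

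**Working it through.** This is a unit conversion. No sample size, power or error rate is involved.

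**Inputs**

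| Quantity | Value as printed | Where |
|---|---|---|
| Study trigger for in-person evaluation | ≥ 0.6 mmol/dL | V. f., Response to Hyperglycemia |
| Camp negative blood ketones | < 0.6 mmol/l | V. d. ii., Hyperglycemia management |
| Camp positive blood ketones | ≥ 0.6 mmol/l | V. d. ii., Hyperglycemia management |

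**Step 1. Put the study trigger in the camp's unit.** One litre is 10 dL, so x mmol/dL = 10x mmol/L.

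0.6 mmol/dL × 10 dL/L = 6.0 mmol/L

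**Step 2. Compare with the camp cut-off.**

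6.0 / 0.6 = 10

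**Step 3. Find the range in which the two rules disagree.**

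6.0 − 0.6 = 5.4 mmol/L, that is, from 0.6 to just under 6.0 mmol/L

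**Step 4. Set out what each rule requires, reading the units literally.**

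| Blood ketones (mmol/L) | Camp rule | Study-clinician visit under V. f. |
|---|---|---|
| Below 0.6 | Negative | Not required |
| 0.6 to just under 6.0 | Positive: site change, injected correction, hourly glucose, activity stopped, physician notified | **Not required** |
| 6.0 and above | Positive, as above | Required |

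**Step 5. Repeat with the unit corrected.** At ≥ 0.6 mmol/L the ratio is 0.6 / 0.6 = 1. The middle row disappears, and the visit is required exactly when the camp rule calls blood ketones positive.

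The documents contain no ketone data, so the number of affected results cannot be estimated.

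**The case against.** The strongest reply is that this is a typing slip which no one on site would follow. The numeral and the inequality match the camp rule, and section V. f. works from ketone checks that camp protocol orders. Staff using the camp definition have no reason to infer a second tier at 6.0 mmol/L. On this view the 5.4 mmol/L gap measures a reading that nobody intended.

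The protocol also has overlapping safeguards that do not depend on the printed unit:

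- Camp treatment of positive ketones continues from 0.6 mmol/l (V. d. ii., kept in force by V. d. iii.).
- Every mandated ketone check prompts a check of the closed-loop system. The infusion set is replaced if its function is in doubt, and a backup system may be started (V. f.).
- A study nurse practitioner or physician is on site day and night. In activity periods, study staff concentrate on volunteers whose telemetry suggests a coming high or low glucose (V. d. iii., V. i.).
- Vomiting brings an in-person study evaluation whatever the ketone value (V. d. iii.).
- Camp providers can phone study staff at once, and a runner is sent if the matter cannot be settled by phone (V. d. iii.).

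The full camp medical manual, Appendix D, was not among the supplied text and may restate the thresholds.

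Most of this stands. It shows that the likely harm is small, and it limits the comparison to the text supplied. It does not make the printed threshold correct. None of these safeguards restores an automatic study-clinician visit triggered by the ketone result, and that visit is the purpose of the line.

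**Conclusion.** The concern holds. The trigger in section V. f. is wrong as written: it equals 6.0 mmol/L, ten times the camp's positive cut-off, and read literally it leaves the required study-clinician visit uncalled from 0.6 to just under 6.0 mmol/L.

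The arithmetic rests on no assumption. That the intended value was 0.6 mmol/L is an inference from the identical numeral and sign and from the absence of any stated reason for a higher study level. It is a strong inference, but the authors should confirm it.

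The weight is modest. No endpoint, estimate or sample-size argument uses the threshold, and the other safeguards leave little practical gap. It should still be corrected, because it is a live decision rule for the safety of young volunteers and should not depend on each reader mending the unit.

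**What to change.** In section V. f., Response to Hyperglycemia, replace mmol/dL with mmol/L. The rule for calling the study physician or nurse practitioner then reads ≥ 0.6 mmol/L and matches the positive-ketone definition in section V. d. ii.

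Any staff training sheet, order set or case report form that carries the threshold should be checked for the same unit. The correction needs no new procedure, measurement, data item or subject.

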#### **V. g. Response to Nausea/Vomiting and Other Medical Needs**

- Minimal nausea was noted in clinical trial of the bi-hormonal closed-loop system to date. In most cases, nausea that occurred did not correspond in time to dosing of glucagon, which is intermittent. However, nausea is a potential side effect of glucagon.
- If vomiting occurs in the setting of glucagon administration (e.g. within 15 minutes of the last dose of glucagon) a study physician or nurse practitioner will be notified and will evaluate the volunteer in person.
- If the volunteer experiences any non-emergent medical concerns outside the scope of diabetes care, he or she will see the camp physician. If the volunteer experiences urgent or emergent medical concerns outside the scope of diabetes care and camp physicians, the camp will escort the volunteer to a local emergency room or call 911 according to camp protocol. If a volunteer in the closed-loop arm of the study is transported away from the camp site for any reason, they will be transitioned to open-loop usual care and their participation in the study will be suspended until they return.

#### **V. h. Monitoring of Closed Loop Device Performance**

- Co-investigators (and bionic pancreas inventors and developers) [name], [name] and/or an engineer trained by them will be readily available by phone for consultation at all times during the course of each experiment and will be able to reach the camp within 1 hour to troubleshoot if necessary.
- They will have the capability of viewing the controller (iPhone) display and diagnostic information remotely during the experiment, in order to monitor and assist in any needed troubleshooting.
- The connection will be secure and password protected, and will be set up so that only viewing of the screen is possible - no input or changes to the controller can be made remotely.
- For privacy reasons, no audio or video connection will be made to the iPhone.

#### **V. i. Supervision by Study Staff**

A study physician or nurse practitioner will be available at the camp at all times during the course of each experiment. Trained study staff will also be continuously monitoring the function of each bionic pancreas via remote telemetry 24 hours a day throughout the experiment from a central location in the camp. The clinicians will also have the capability of remotely viewing the controller display on their iPhone or iPad and evaluating diagnostic information during the experiment to facilitate clear communication with nurses.

## **V. j. Modifications to the Control Algorithm**

Certain parameters of the control algorithm may be adjusted between a proposed “dry run” with a small number of subjects prior to the main study and the start of the main study, as approved in the Investigational Device Exception, but no parameters may be adjusted once the main study has started.

## **VI. Biostatistical Analysis**

### **VI. a. Data Collected**

#### **Prior to start of experiment:**

- Age
- Sex
- Race and ethnicity
- Date of last menstrual period in female volunteers post-menarche
- Urine HCG for female volunteers post-menarche
- Date of diabetes diagnosis
- Medical, surgical, and social history, allergies, and review of systems relevant to inclusion and exclusion criteria
- Medications (prescription and non-prescription) and date of last change in medication regimen
- Insulin regimen (basal rate, sensitivity factor, and carbohydrate ratio)
- Average total daily dose of insulin in the last 30 days as available (from pump history)
- Duration of insulin pump use
- Usage of CGM, if any (type of CGM, days per month worn, usage of data, whether insulin is dosed based on CGM alone, alarm settings)
- History of insulin types used (beef insulin, pork insulin, regular human insulin, NPH insulin, ultralente insulin, insulin aspart, insulin lispro, insulin glulisine, insulin detemir, insulin glargine)
- Height and weight
- Blood pressure
- Hemoglobin A1c

#### **During the monitoring of usual care period:**

- CGMG (CGM glucose) every five minutes from the DexCom G4 Platinum CGM
- HemoCue BG measurements before meals, snacks, bedtime, 12:00 AM and 3:45 AM
- Any additional HemoCue BG values
- Estimated carbohydrate intake (from camp healthcare provider documentation)
- Exercise and activity level (from camp schedule)
- Number of hypoglycemic events and nadir BG for each (from camp healthcare provider documentation)
- Number of carbohydrate interventions for hypoglycemia (from camp healthcare provider documentation)
- Total daily dose of insulin (from insulin pump download)

#### **During the closed-loop study period:**

- CGMG every five minutes from the DexCom G4 Platinum CGM
- HemoCue BG measurements before meals, snacks, bedtime, 12:00 AM and 3:45 AM
- Any additional HemoCue BG values
- Estimated carbohydrate intake (from camp healthcare provider documentation)
- Exercise and activity level (from camp schedule)
- Number of hypoglycemic events and nadir BG for each (from camp healthcare provider documentation)
- Number of carbohydrate interventions for hypoglycemia (from camp healthcare provider documentation)
- Insulin and glucagon doses administered by the control system
- Timing of meal announcements and size of meals announced
- Number of meal announcements
- Time between meal announcement and start of meal
- Meal and snack number, and timing
- Bionic pancreas downtime – number, timing, and duration of periods offline, reasons for being offline (CGM sensor loss, system crash, communication problem between CGM and bionic pancreas, communication problem between bionic pancreas and pumps, pump malfunction, tubing occlusion, infusion set failure/pulled out)
- Insulin bolus dosing in open-loop mode during CGM downtime
- Basal rate adjustments, including suspensions, during bionic pancreas downtime

**For consenting non-participants:**

- BG measurements before meals, snacks, bedtime, and 12:00 AM
- Any additional BG values
- Estimated carbohydrate intake (from camp healthcare provider documentation)
- Exercise and activity level (from camp schedule)
- Number of hypoglycemic events and nadir BG for each (from camp healthcare provider documentation)
- Number of carbohydrate interventions for hypoglycemia (from camp healthcare provider documentation)

**VI. b. Study Endpoints**

**Co-primary endpoint analysis:**

- Difference in average BG between closed-loop and open-loop periods as determined from all scheduled HemoCue measurements. This mean will be evenly weighted across the daytime and nighttime hours.
- Difference between closed-loop and open-loop in the percentage of the above subset of BG values less than 70 mg/dl.

**Secondary endpoint analyses - BG:**

- All of following metrics will be generated from the HemoCue data during the closed-loop period and the usual care period, and the difference between the two periods will be reported unless otherwise specified:
- Average BG as determined from all HemoCue measurements taken during the day/nighttime including all extra measurements taken before meals, taken during exercise, and taken for hypoglycemia monitoring.

- Percentage of the above subset of BG values less than 70 mg/dl.
- Average BG as determined from the pre-meal, before bed, 12:00 AM, and 3:45 AM HemoCue measurements (6measurements per day)
- Percentage of the above subset of BG values less than 70 mg/dl.
- Percentage of subjects with mean BG < 154 mg/dl using all BG values
- Difference in the percentage of subjects with mean BG < 154 mg/dl using before meal and before bedtime BG values only
- Percentage of study days with mean BG < 154 mg/dl
- Number of hypoglycemic events as determined from all HemoCue measurements
- Nadir BG for each hypoglycemic event as determined from HemoCue measurements
- Fraction of scheduled BG measurements within each of the following glucose ranges as determined from all HemoCue measurements :
  - < 70 mg/dl
  - 70-120 mg/dl
  - 70-180 mg/dl
  - >180 mg/dl
  - >250 mg/dl
- Risk of hypoglycemia and hyperglycemia >180 mg/dl and >250 mg/dl during hours with vs. without bionic pancreas downtime
- Difference of outcome measures on day 1 vs. remaining days (days 2-5) and on day 1-2 vs. on remaining days (days 3-5)
- Difference in average BG as determined from the pre-meal, before bed, and 12:00 AM measurements between the non-participants and the open-loop and closed-loop arms.
- Percentage of the above subset of BG values less than 70 mg/dl between the non-participants and the open-loop and closed-loop arms.
- Difference in the percentage of subjects with mean BG < 154 mg/dl using before meal and before bedtime BG values only between the non-participants and the open-loop and closed-loop arms.
- Number of hypoglycemic events as determined from all BG measurements
- Nadir BG for each hypoglycemic event as determined from BG measurements
- Fraction of scheduled BG measurements within each of the following glucose ranges as determined from all BG measurements :
  - < 70 mg/dl
  - 70-120 mg/dl
  - 70-180 mg/dl
  - >180 mg/dl
  - >250 mg/dl

